4.7.3.2 Physical examination

Each physical examination will include the following physical observations/measurements: head, heart, lung, abdomen, musculo/skeletal, skin, neurological and mental status.

Physical examination findings will be assessed as normal or abnormal.

Number and percentage of participants with complete abnormal physical examination will be summarized at each planned visit during the treatment emergent period.

4.7.3.3 Neurological examination

Each neurological examination will include, but are not limited to:

• cranial nerve examination: olfactory, optic, oculomotor, trochlear, trigeminal, abducens, facial, vestibulocochlear, glossopharyngeal, vagus, accessory, hypoglossal)

- extrapyramidal features: postural tremor, rest tremor, intention tremor, cogwheel rigidity, lead pipe rigidity, bradykinesia, postural deficit, dystonia, other
- gait examination: antalgic, staggering, steppage, waddle, difficulty initiating, glue footed, toe walking, other
- coordination examination: finger to nose test, rapid alternating movements, heel to shin, tandem gait
- motor examination (tone): spasticity, rigidity, paratonia, other, decreased muscle tone
- peripheral nervous system (sensory disturbances)
- reflexes examination
- strength examination: heel walking, sit to stand test, toe walking, other motor abnormality

These examination findings will be assessed as normal or abnormal.

Number and percentage of participants with abnormal neurological examination will be summarized by location (cranial nerve, Extrapyramidal features, motor, Peripheral nervous system strength, reflex, sensory, coordination, gait) at each planned visit during the treatment emergent period.

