#### **9.4.6 Physical examination**

Whenever possible, the same physician or appropriately trained member of the site study team (in countries/states which permit nurse practitioners or physician assistants to perform physical examinations under the supervision of a physician) should perform the physical examination at all study visits. The findings of each examination will be recorded.

A complete physical examination will include a thorough review of all body systems to collect physical observations/measurements.

A mental status evaluation will be performed as a part of the complete physical examination and should include a Mini Mental State Examination (MMSE) or an equivalent local standard method for assessment of the cognitive state of a patient, provided the method covers all the areas assessed by MMSE.

A full standard basic neurological examination will be performed as a part of the complete physical examination. Results will be documented in the eCRF pages dedicated to neurological examination. For details, please refer to the Study Reference Manual.

The Investigator will evaluate and access clinical findings as normal, abnormal but not clinically significant, or abnormal and clinically significant.

Complete physical examination will be performed at screening, Months 18 and 24. At screening, height will be measured without shoes and body weight will be measured without shoes or heavy clothing (see [Section 1.3](#) and [Section 1.4](#)).

Abbreviated physical examinations will focus on areas important for assessment of AEs if necessary.

Abbreviated physical examinations will be performed at the run-in visit, Months 0, 1, 3, 6, 9, 12, 15, 21, and 25 (see [Section 1.3](#) and [Section 1.4](#)).

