Potentially clinically significant abnormality (PCSA) analyses will be performed based on the PCSA list in effect at Sanofi at the time of the database lock. For parameters for which no PCSA criteria are defined, similar analyses will be done using the normal range, if applicable.

For parameters defined as efficacy endpoints, PCSA summaries will not be provided.

Analyses according to PCSA will be performed based on the worst value during the treatmentemergent period, using all measurements (either local or central, either scheduled, nonscheduled or repeated).

For laboratory variables, vital signs and ECG variables above, the incidence of participants with at least one PCSA during the treatment-emergent period will be summarized regardless of the baseline level and according to the following baseline status categories:

- Normal/missing
- Abnormal according to PCSA criterion or criteria

For ECG, the incidence of participants with at least one abnormal ECG during the treatmentemergent period will be summarized regardless of the baseline level and according to the following baseline status categories:

- Normal/missing
- Abnormal

Additional analyses for drug-induced liver injury

The following additional analyses will be performed for drug-induced liver injury:

- A graph of the distribution of peak values of ALT versus peak values of total bilirubin during the treatment-emergent period will be provided.
- For each liver function test (eg, ALT), participants having experienced a PCSA (eg, ALT >5 ULN) will be summarized using the following categories: Returned to baseline PCSA status (or returned to value \le ULN in case of missing baseline) before last IMP dose, Returned to baseline PCSA status after last IMP dose, Never returned to baseline PCSA status, No assessment after elevation. This summary will be performed by categories of elevation (ALT >3, >5, >10, >20 ULN).

The incidence of liver related AEs will be summarized by study intervention group. The selection of PT will be based on SMQ Hepatic disorder.

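### The physical and neurological examination tables take no account of screening status, so a new abnormality is diluted by abnormalities that were already there

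*SAP*

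**What the plan says.** SAP 4.7.3.3 states the neurological summary as "Number and percentage of participants with abnormal neurological examination will be summarized by location", shown "at each planned visit during the treatment emergent period". Results have two levels only: "These examination findings will be assessed as normal or abnormal". SAP 4.7.3.2 has the same form: "Number and percentage of participants with complete abnormal physical examination will be summarized at each planned visit during the treatment emergent period". Neither section has a split by baseline status, a shift table or a count of new abnormalities.

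Neighbouring sections do use baseline. In SAP 4.7.3.1 the incidence of abnormal ECGs "will be summarized regardless of the baseline level and according to the following baseline status categories", these being normal/missing and abnormal. The same split applies to potentially clinically significant laboratory, vital sign and ECG values. SAP 4.7.3.4 counts new onset of abnormal eye findings, and SAP 4.7.3.5 counts participants whose BDI-II worsened from baseline.

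A pre-treatment examination exists. Protocol 9.4.6 says "Complete physical examination will be performed at screening, Months 18 and 24" and "A full standard basic neurological examination will be performed as a part of the complete physical examination".

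Two other statements bear on the point. SAP 5.3 (Appendix 3) says that baseline safety parameters will be shown with the safety summaries. SAP 4.7 says that the safety analysis is essentially descriptive, with no testing.

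**The concern.** A safety table for an examination should help the reader see whether participants became abnormal on treatment. These two tables show only who is abnormal at a visit. Someone with a gait or sensory abnormality at screening that persists is counted at Months 18 and 24 like someone who developed it on study. Because the scale is binary, such a participant also cannot register any worsening.

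The examination matters for this compound. Protocol 4.1.1 reports that venglustat crossed the blood-brain barrier in preclinical work, Protocol 9.2.3 lists physical examination findings among the safety endpoints, and Protocol 9.4.6 gives the neurological examination its own eCRF pages. What is at stake is readability: a modest excess of new abnormalities could look small against a common background of old ones.

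**Working it through.** **No plan figure to reproduce.** The documents give no prevalence of abnormal examinations, no expected new-onset rate, and no power or alpha for safety. The size below is an illustration on stated assumptions.

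**Set-up.** Let p be the proportion of each arm abnormal at screening (equal in expectation by randomization), s the share of those still abnormal at the visit, and q0, q1 the new-onset rates on placebo and venglustat among participants normal at screening.

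- The planned table shows ps + (1−p)q0 against ps + (1−p)q1.
- Its risk difference is (1−p)(q1−q0).
- A table restricted to participants normal at screening shows q0 against q1 whatever p is.

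**Assumed values.** q0 = 2%, q1 = 6% (true difference 4.0 points, true ratio 3.0), s = 1.

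| p | Placebo | Venglustat | Difference (points) | Ratio |
|---|---|---|---|---|
| 0% | 2.0% | 6.0% | 4.0 | 3.00 |
| 1% | 3.0% | 6.9% | 4.0 | 2.33 |
| 5% | 6.9% | 10.7% | 3.8 | 1.55 |
| 10% | 11.8% | 15.4% | 3.6 | 1.31 |
| 20% | 21.6% | 24.8% | 3.2 | 1.15 |
| 30% | 31.4% | 34.2% | 2.8 | 1.09 |

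At p = 10%: 0.10 + 0.90 × 0.02 = 0.118 and 0.10 + 0.90 × 0.06 = 0.154. The difference shrinks only by the factor 1−p. The ratio falls much faster, because pre-existing cases make up 0.10/0.118 = 85% of abnormal placebo participants. If half of the baseline abnormalities resolve (s = 0.5), the ratio at p = 10% is 10.4%/6.8% = 1.53.

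**Does an arm-level baseline row solve it?** Take p = 10% and s = 0.5. The venglustat arm moves from 10% at screening to 0.05 + 0.90 × 0.06 = 10.4% at the visit, an apparent change of 0.4 points, while 0.90 × 6% = 5.4% of the arm is newly abnormal. Resolved and new abnormalities offset each other, and only a within-participant count separates them.

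**Would the two rows cover the same participants?** Probably not. SAP 5.4 summarises these examinations by protocol planned visit, that is, Months 18 and 24. SAP Table 1 says that no post-baseline Stage 2 MRI was available when the study stopped, and Protocol 9.4.1 places the only post-baseline Stage 2 MRI at Month 18. The Month 18 and 24 rows should therefore come largely from Stage 1, whereas a baseline row on the extended combined safety population covers both stages.

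**The case against.** The strongest reply is that little is lost.

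- **Baseline will be shown.** A reader might infer that the screening examination is hidden and cannot be subtracted. SAP 5.3 does not support that: on its ordinary reading, an arm-level baseline appears beside these summaries. This stands. What is missing is the within-participant comparison.
- **New findings have another route.** SAP 4.7.2 tabulates events that developed or worsened on treatment. Protocol 10.4.2 restricts adverse event recording for laboratory, vital sign, ECG and ophthalmic abnormalities but does not list physical or neurological ones, so the comparison with ECG and eye findings is not fully like for like. Lens clarity and BDI-II are also named as change endpoints. This stands as mitigation. It still depends on the investigator reporting the sign as an adverse event.
- **Prevalence may be low.** A reader might infer that old abnormalities fill these tables. No document gives a prevalence. The neurological table is by location, where prevalence could be small, and any abdominal findings from enlarged kidneys would affect only the physical examination table. This stands: near 0% the point has almost no weight.
- **No test is planned.** Power for a comparison of these proportions would gauge something that the SAP does not intend to do, so none is offered here.

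**Conclusion.** The point holds as one of presentation. Both tables ignore screening status although the screening examination is collected and adjacent sections use baseline. The consequence is dilution. It should not be read as bias between arms: with randomization, pre-existing abnormalities are expected to be balanced, and the risk difference keeps its direction.

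The size depends on an unknown prevalence. Under the assumed 2% versus 6% new onset with persisting abnormalities, the displayed ratio is 2.33 at 1% prevalence and 1.31 at 10%, against a true 3.0, while the difference falls only from 4.0 to 3.6 points at 10%. The adverse event tables and the arm-level baseline soften this without replacing a new-onset count. As safety is descriptive, the importance is minor.

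**What to change.** In SAP 4.7.3.2 and 4.7.3.3 add, by arm, the number and percentage of participants with an abnormal examination in the treatment-emergent period, split by screening status (normal/missing versus abnormal), as SAP 4.7.3.1 does for ECG. For the neurological examination, also give the count of new abnormalities by location, meaning participants normal or missing at that location at screening and abnormal there afterwards. Use as denominator the participants in that screening category with a treatment-emergent examination, so that numerator and denominator refer to the same people. The planned by-visit tables can stay.

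The cost is a few sentences in the SAP, some programming and a few extra table rows. No new data are needed.

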4.7.3.4 Ophthalmological examination

The full ophthalmological examination includes best corrected visual acuity (BCVA), slip-lamp examination, and examination of the cornea, lens, and retina. The examination should include pupil dilation and evaluation of the lens according to the lens opacities classification system III (LOCSIII), before implementation of protocol amendment 5. For opacities present at baseline/previous visit, changes in LOCSIII score of ≥ 0.5 (respectively ≥ 1) for nuclear opalescence, ≥ 0.8 (respectively ≥ 1) for cortical opacification, or ≥ 0.5 (respectively ≥ 1) for posterior subcapsular opacification compared with baseline or previous assessment will be considered as a worsening. After protocol amendment 5, the LOCSIII examination is replaced by the WHO simplified cataract grading system. For opacities present at baseline/previous visit, increases in WHO grade ≥ 1.0 for nuclear opacification, cortical opacification, or posterior subcapsular opacification compared with baseline or previous assessment will be considered as a worsening.

Secondary safety endpoints include change in the lens clarity by ophthalmological examination during the treatment emergent period.

Number and percentages of participants with abnormal ophthalmological examination on any eye at any time (whether present at screening or not) as well as number and percentages of participants with any new onset of abnormal ophthalmological examination on any eye during the treatment emergent period as per investigator (site ophthalmologist) assessment will be summarized along with a description of lens opacity according to LOCSIII or the WHO classification.

The decrease in BCVA will also be presented on any eye at any time (whether present at screening or not). This decrease will be presented according to 1, 2 or 3 lines (defined as 0.1, 0.2 or 0.3 increases in LogMAR) (see [7]).

4.7.3.5 Depression (BDI-II) examination

Depression will be monitored during the study by using the BDI-II.

Secondary safety endpoints include change in score of BDI-II during the treatment emergent period.

Descriptive statistics for values and changes from baseline in BDI-II total score will be presented for each time point during the on-treatment period (see Section 4.1). All measurements will be assigned to analysis windows defined in Table 12.

The worst (highest) BDI-II total score during the treatment emergent period will be categorized and summarized using the number and percentage of participants in each study intervention group within each of the following categories:

- 0-13 (minimal depression)
- 14-19 (mild depression)
- 20-28 (moderate depression)
- 29-63 (severe depression)

The worst (highest) score for suicidal thoughts (Item 9 of BDI-II) during the treatment emergent period will be summarized within each of the following categories:

- I don't have any thoughts of killing myself
- I have thoughts of killing myself, but I would not carry them out
- I would like to kill myself
- I would kill myself if I had the chance

In addition, the number of participants with BDI-II worsening from baseline during the treatment emergent period will be summarized.

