Randomization			X										

	Screening period		Blinded treatment period a										Follow-up (off-treatment)
	Initial screening	Run-in	3 (Baseline)	4	5	6	7	8	9	10	11	12 a, w (End of treatment)	13 b
Visit	1	2											
Months	-1	-0.5	0	1	3	6	9	12	15	18	21	24	25
Day (window [days])	-30 to -16 u (+3)	-15 (±3)	1 (±3)	30 (±7)	90 (±7)	180 (±7)	270 (±7)	360 (±7)	450 (±7)	540 (±7)	630 (±7)	720 (±7)	750 (-7 to +21)
PROr													
BPI			X	X	X	X	X	X	X	X	X	X	
BFI			X	X	X	X	X	X	X	X	X	X	
PGIS		X	X		X			X		X		X	
PGIC					X			X		X		X	
EQ-5D-5L			X		X	X		X		X		X	
Dispense IMP/placebo		X v	X	X	X	X	X	X	X	X	X		
Call IXRS/IWRS	X	X	X	X	X	X	X	X	X	X	X	X	X
IMP accounting & compliance			X	X	X	X	X	X	X	X	X	X	
Biobanking s			X					X				X	
Pharmacogenetic sample			X										
Concomitant medication	X	X	X	X	X	X	X	X	X	X	X	X	X
AEs/SAE f	X	X	X	X	X	X	X	X	X	X	X	X	X

AEs = adverse events; AESI = adverse events of special interest; BCVA = best corrected visual acuity; BDI-II = Beck Depression Inventory-II; BFI = Brief Fatigue Inventory; BP = blood pressure; BPI = Brief Pain Inventory; CT = computed tomography; ECG = electrocardiogram; EQ-5D-5L = EuroQoL 5-dimension 5-level; FSH = follicle stimulating hormone; GSL = glycosphingolipid; IMP = investigational medicinal product; MRI = magnetic resonance imaging; PGIC = Patient Global Impression of Change; PGIS = Patient Global Impression of Severity; PK = pharmacokinetic; PRO = Patient Reported Outcome; SAEs = serious AEs; TKV = total kidney volume; US = ultrasonography; WHO = World Health Organization; WOCBP = women of childbearing potential.

- a If a patient discontinues treatment with IMP early during the core treatment period, the patient will have an End-of-Treatment/Early Withdrawal (EOT/EW) Visit within 7 days and a Follow-up Visit 30 days after the last dose of IMP. In addition, every effort will be made to have the patients return to the site at the time corresponding to their scheduled visits, particularly the Month 18 Visit and the Month 24 Visit. If the patient does not agree to a site visit, they will be contacted by telephone to inquire about safety status.

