#### **10.3.4 Handling of patients after permanent treatment discontinuation**

Patients will be followed-up according to the study procedures specified in this protocol up to the scheduled date of study completion, or up to recovery or stabilization of any AE to be followed-up as specified in this protocol, whichever comes last.

All cases of permanent treatment discontinuation must be recorded by the Investigator in the appropriate pages of the eCRF when considered as confirmed.

Patients who prematurely and permanently discontinue study medication should complete rapidly (within 7 days) an end-of-treatment (EOT) assessment visit.

Stage 1: EOT visit should include all procedures of Visit 12 and additionally a PK sample should be collected. In 30 days, a premature Follow-up visit (all procedures of Visit 13) should be performed.

Stage 2: EOT visit should include all procedures of Visit 12. In 30 days, a premature Follow-up visit (all procedures of Visit 13) should be performed.

In addition, for both Stage 1 and Stage 2:

1. Investigator should ask patient who prematurely and permanently discontinued study medication to continue study visits for safety and efficacy assessments (including PRO questionnaires) up to and including the last scheduled visit, if possible.

2. If the patient refuses to attend all scheduled visits and to continue answering all PRO questionnaires, Investigator should ask the patient to continue answering questions of “Daily symptoms of ADPKD” diary and to return to the site at 18 months (to have at least an MRI, blood sample for eGFR evaluation, urine analysis [for urine protein and osmolality], as well as safety assessments performed) and at 24 months (to have blood sample for eGFR evaluation, urine analysis [for urine protein and osmolality], and safety assessments performed).

For patients participating in mGFR substudy of the Stage 2, mGFR measurement should be performed at 24 months.

Patients who withdraw from the study due to pregnancy should be followed throughout the pregnancy up to approximately 6 to 8 weeks beyond the estimated delivery date so that the outcome of the pregnancy is determined. Additional follow-up information may be requested about the baby until at least one year after the birth of the baby, due to potential risk of abnormalities not present at birth. See [Appendix A](#) for guidance.

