#### **11.4.3 Analyses of safety data**

The observation period will be divided into 4 periods:

- The pretreatment period is defined as the time from the signed informed consent date up to the day prior to the first double-blind IMP administration.

- The on-treatment period is defined as the time from the first administration of the IMP to the last administration of the IMP +1, including any temporary treatment discontinuation period, if any.
- The residual treatment period is defined as the time from the day after the last IMP administration plus 30 days or up to the first visit in the long-term extension study, whichever comes earlier:
  - The treatment-emergent period will include both the on-treatment and the residual treatment periods.
- The post-treatment period is defined as the period of time starting the day after the end of the TEAE period up to the end of the study.

All safety analyses will be performed on the safety population using the following common rules:

The baseline value is defined generally as the last available value before first IMP administration.

The following definitions will be applied to laboratory parameters, vital signs and ECG.

- The potentially clinically significant abnormality (PCSA) values are defined as abnormal values considered medically important by the Sponsor according to predefined criteria/thresholds based on literature review and defined by the Sponsor for clinical laboratory tests, vital signs, and ECG.
- Potentially clinically significant abnormality criteria will determine which patients had at least 1 PCSA during the treatment-emergent period, taking into account all evaluations performed during the treatment emergent period, including unscheduled or repeated evaluations, local and central evaluations. The number of all such patients will be the numerator for the treatment emergent period PCSA percentage.

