4 STATISTICAL ANALYSES

4.1 GENERAL CONSIDERATIONS

In general, continuous data will be summarized using the number of observations available, mean, standard deviation (SD), median, [Q1, Q3] minimum, and maximum. Categorical and ordinal data will be summarized using the count and percentage of participants.

The baseline value is defined as the last available value before or equal to the first dose of double-blind investigational medicinal product (IMP). For participants randomized but not exposed, the baseline value is defined as the last available value before or equal to the date and time of randomization.

Baseline eGFR is defined for each participant as the average of eGFR values assessed prior or equal to first IMP, or randomization for participants randomized and not exposed.

Baseline of patient daily diaries scores is defined for each participant as the average of the assessments during the 7 days prior the 1st IMP or prior randomization for participants randomized and not exposed.

Baseline of urine osmolality is defined as the average of the 3 separate assessments within the 3 days prior or equal to the baseline visit (Visit 3).

Primary efficacy analyses will be conducted on Stage 1 ITT population and on combined Stage 1 and Stage 2 ITT populations (see Section 3), including all data available at the time of database lock from baseline to Month 24:

• Participants from Stage 2 with an eGFR between 30 and 44.9 mL/min/1.73 m² at screening will not be included in the primary efficacy analysis. A supplemental descriptive efficacy analysis on these participants will be performed separately (see Section 3 and Section 4.3.2.4).

Safety analyses will be conducted in the extended combined Stage 1 and Stage 2 population (see Section 3) including all data available from baseline to the end of the 24-month double-blind treatment period. Unless otherwise specified, analyses will be performed by intervention group (and overall for baseline and demographics characteristics).

Observation period

The observation period will be divided into 4 segments:

- The **pre-treatment period** is defined as the period up to first IMP administration.
- The **treatment-emergent** (TE) **period** is defined as the period from the first IMP administration up to the last IMP administration in EFC15392 study +30 days or up to the first visit in LTS15823 study, whichever comes earlier. The treatment-emergent period includes the following 2 periods:

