- The **on-treatment period** is defined as the period from the first IMP administration to the last administration of the IMP +1 day.
- The **residual treatment** period is defined as the period from the end of the ontreatment period to the end of the treatment-emergent period.
- The **post-treatment period** is defined as the period from the end of the treatmentemergent period.

The on-study observation period is defined as the time from the first administration of the IMP until the end of the study (defined as the last scheduled visit for those who completed the study and the end-of-study date collected on electronic case report form (e-CRF) page "Completion of End of Study" for those who did not complete the study. If death is the end-of-study reason, date of death will be used).

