4.7.3 Additional safety assessments

4.7.3.1 Laboratory variables, vital signs and electrocardiograms (ECGs)

The following laboratory variables, vital signs and electrocardiogram (ECG) variables will be analyzed. They will be converted into standard international units.

- Hematology:
 - Red blood cells and platelets and coagulation: hemoglobin, hematocrit, erythrocyte count, platelet count, prothrombin time (PT), prothrombin international normalized ratio (INR), activated partial thromboplastin time (aPTT).

- White blood cells: white blood cell count, neutrophils, lymphocytes, monocytes, basophils, eosinophils.
- Clinical chemistry:
 - Metabolism: glucose, protein, albumin.
 - Electrolytes: sodium, potassium, chloride, bicarbonate, calcium.
 - Renal function: creatinine, blood urea nitrogen, serum cystatin C.
 - Liver function: alanine aminotransferase, aspartate aminotransferase, alkaline phosphatase, gamma glutamyl transferase, total and direct bilirubin.
 - Pregnancy test: Serum β-human chorionic gonadotropin (all female participants).
- Urinalysis:
 - Urinalysis for quantitative analysis: pH, specific gravity, proteins, and glucose.
- Vital signs: heart rate, systolic and diastolic blood pressure, weight.
 - For all seated BP measurements, SBP and DBP will be analyzed using the average of the 3 to 5 separate measurements at each visit.
- ECG variables: heart rate, PR, QRS, QT, and corrected QTc (according to Bazett/Fridericia).

Data below the lower limit of quantitation/detection limit (LLOQ) will be replaced by half of the LLOQ, data above the upper limit of quantification will be replaced by ULOQ value.

Quantitative analyses

For all laboratory variables, vital signs and ECG variables above, descriptive statistics for results and changes from baseline will be provided for each visit, the last value and the worst value (minimum and/or maximum value depending on the parameter) during the on-treatment period.

All laboratory parameters (except urinalysis parameters) and vital signs parameters (except weight and height) will be summarized using the analysis windows as defined in Table 12. Urinalysis, ECG and weight will be summarized by planned visit using central measurements only.

Analyses according to PCSA

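### SAP 4.7.3.5 summarises BDI-II change over the on-treatment period although the endpoint is defined over the treatment-emergent period; blood pressure has the same mismatch

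*SAP*

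**What the plan says.** SAP 4.1 sets two periods. The on-treatment period "is defined as the period from the first IMP administration to the last administration of the IMP +1 day"; protocol 11.4.3 has the same rule ("the time from the first administration of the IMP to the last administration of the IMP +1"). The treatment-emergent period runs "up to the last IMP administration in EFC15392 study +30 days or up to the first visit in LTS15823 study", whichever is earlier.

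On BDI-II, SAP 4.7.3.5 states: "Secondary safety endpoints include change in score of BDI-II during the treatment emergent period". The paragraph after it presents values and changes from baseline "for each time point during the on-treatment period (see Section 4.1").

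On blood pressure, SAP 4.5.1 lists change in SBP and DBP over the treatment-emergent period and points to 4.7.3.1. That section gives results and changes from baseline for each visit, the last value and the worst value ("minimum and/or maximum value depending on the parameter) during the on-treatment period").

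On timing, protocol 10.3.4 says that patients who permanently stop study medication early "should complete rapidly (within 7 days) an end-of-treatment (EOT) assessment visit", with all Visit 12 procedures. The flow chart footnote agrees: "the patient will have an End-of-Treatment/Early Withdrawal (EOT/EW) Visit within 7 days and a Follow-up Visit 30 days after the last dose of IMP". Visit 12 includes both vital signs and BDI-II.

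**The concern.** An endpoint and the table that reports it should cover the same period. Here the endpoint runs to 30 days after the last dose and the change table stops after 1 day. The assessment that falls between the two cut-offs is the EOT visit of a patient who stopped early. It is normally that patient's longest-exposure assessment, and the visit meant to record the state at the end of treatment. A Month 24 completer is dosed at the clinic on the visit day (protocol 10.1.2.2) and keeps the value; an early stopper may not.

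The point has more reach in this trial than in most. SAP version 2 was written after the decision to discontinue the study for futility, so many final assessments are likely to be premature EOT visits.

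**Working it through.** The plan gives no figure to reproduce. The check compares definitions and counts days.

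**Endpoint period against summary period**

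| Output | Period in the endpoint definition | Period in the summary |
|---|---|---|
| BDI-II change from baseline | treatment-emergent (SAP 4.4.3, 4.7.3.5) | on-treatment (4.7.3.5) |
| SBP/DBP change: last and worst values | treatment-emergent (4.5.1) | on-treatment (4.7.3.1) |
| SBP/DBP change: by visit | treatment-emergent (4.5.1) | on-treatment on one reading of 4.7.3.1 |
| Worst BDI-II category, worst item 9, BDI-II worsening | treatment-emergent | treatment-emergent (4.7.3.5) |
| PCSA counts, abnormal ECG | none stated | treatment-emergent (4.7.3.1) |

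The first three rows do not match. Protocol 11.4.3.2 planned the visit, last and worst summaries of laboratory data and vital signs over the treatment period, which protocol 9.2.3 runs to 30 days after the last dose. Neither SAP Table 1 nor Table 9 records a narrowing.

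**Day count.** Let d be the days from last dose to EOT, assuming the 7-day allowance runs from the last dose.

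- Allowed: d = 0 to 7, which is 8 days.
- Inside the on-treatment period (d ≤ 1): days 0 and 1.
- Outside it: days 2 to 7, which is 6 of the 8 days.
- Inside the treatment-emergent period (d ≤ 30): all 8 days, unless a first LTS15823 visit comes earlier.

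**Share lost.** Let p be the proportion of premature EOT visits held on days 2 to 7. If all are on day 0 or 1, p = 0%. If all are on days 2 to 7, p = 100%. If they were spread evenly, p = 6/8 = 75%. Neither document gives the distribution, so the even spread is only an illustration.

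**Reach.** The DMC futility review was on 14 May 2021 (SAP 4.9.2). Counting randomization as Day 1, Day 720 falls 719 days later. Only participants randomized by 14 May 2021 − 719 days = 26 May 2019 could have reached it by that date; the first randomization was on 11 February 2019. Stage 2 had no post-baseline MRI at discontinuation (SAP 4.4.2.2), and that MRI is due at Month 18, so a Stage 2 EOT visit at that point would be premature. Stage 2 is 400 of 640 planned participants: 400/640 = 62.5%, if enrollment went as planned.

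**What a longer period lets in.** The flow charts schedule vital signs at Visit 13 but not BDI-II. Visit 13 is nominally 30 days after the last dose with a window of −7 to +21 days, so days 23 to 51. A blood pressure taken there on days 23 to 30 would fall inside the treatment-emergent period.

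**The case against.** The strongest reply is that little is lost. Safety analyses are descriptive with no testing (SAP 4.7). The worst BDI-II category, worst item 9 score and number of participants with BDI-II worsening all use the treatment-emergent period, and the last of these is itself a change-from-baseline output. PCSA counts use the worst treatment-emergent value from all measurements. Showing means on treatment and abnormalities over the longer period is a coherent split that keeps off-drug values out of the means, and the +1-day rule comes from the protocol.

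Most of this stands, and it rules out several stronger readings.

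- *Most EOT values are lost.* Not supported: that needs an assumed distribution of visit days. Patients in a sponsor-led stop may well have taken the last dose on the visit day or the day before.
- *A patient who stops because of mood or a laboratory change loses the value that records it.* Not supported: a value that prompts stopping is normally measured before the stop, unscheduled values count toward the last and worst on-treatment values (SAP 5.4), and EOT values remain in the treatment-emergent outputs.
- *Any ECG after Month 6 disappears.* Not supported: an EOT tracing stays in the ECG PCSA and abnormal-ECG counts. The by-visit ECG table uses planned visits, and no rule says where a premature EOT tracing would go.
- *All by-visit laboratory, vital-sign and ECG summaries are cut.* Not certain: in 4.7.3.1 the period may qualify only the last and worst values.

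Two limits apply to the point itself. Under SAP 5.4 a scheduled-visit value takes precedence within a Table 12 window, so a longer period alone does not guarantee that every EOT value appears by visit. Also, 4.7.3.1 withholds PCSA summaries from parameters defined as efficacy endpoints, and 4.5.1 lists SBP and DBP among the exploratory efficacy endpoints. Whether blood pressure keeps its PCSA counts depends on how that rule is meant.

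The reply does not remove the mismatch: the SAP chose the treatment-emergent period for these endpoints and then reports their change over another.

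**Conclusion.** The mismatch is real and specific. The BDI-II change endpoint, and the SBP/DBP change endpoints at least for last and worst values, are summarised over a shorter period than the SAP defines for them. EOT assessments of early stoppers made 2 to 7 days after the last dose, which the protocol allows, are therefore excluded from these change summaries.

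The size cannot be fixed: 0% to 100% of premature EOT visits, depending on the gap from last dose to EOT. The early stop makes such visits likely to be common, but the documents do not describe the close-out. The conclusion assumes that the 7 days run from the last dose. It does not touch the efficacy analyses. A reader might infer that safety information is lost or that all laboratory and ECG summaries are wrong; the documents do not support that, because the treatment-emergent outputs keep these values and the SAP states no treatment-emergent change endpoint for those other variables.

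**What to change.** - In SAP 4.7.3.5, replace the on-treatment period with the treatment-emergent period for BDI-II values and changes from baseline.
- In SAP 4.7.3.1, state that SBP and DBP change summaries use the treatment-emergent period, to match 4.5.1.
- Say in 5.4 whether a premature EOT value counts as a scheduled-visit value under the Table 12 rules.
- Optional, for the other laboratory, vital-sign and ECG variables: a cut-off that keeps protocol-compliant EOT values in the last and worst values, for example last dose + 7 days. Neither document uses that cut-off, so this is a preference.

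The cost is SAP wording and a date cut-off in programming, with no new data. The downside is small. Some summarised values will have been taken a few days after the last dose. For SBP and DBP, the off-treatment Visit 13 value may enter the last and worst values. BDI-II is not scheduled at Visit 13, so that visit adds no scheduled BDI-II value, though a patient who stops and stays on the regular visit schedule could contribute one within the 30 days.
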